5. GENERAL METHODOLOGY AND CONVENTIONS

Methodology for summary and statistical analyses of the data collected in this study is described here. The SAP may modify what is outlined in the protocol where appropriate; however, any major modifications of the primary endpoint definitions or their analyses will also be reflected in a protocol amendment.

Cohort 1, Cohort 2, and Cohort 4: To facilitate rapid review of data in real time, the majority of Pfizer/BioNTech staff will be unblinded to the study intervention allocation.

Cohort 3: Given the single study intervention arm, both groups are unblinded to the majority of Pfizer staff involved in the conduct of the study.

All Cohorts: All laboratory testing personnel performing serology assays will remain blinded to the study intervention assigned/received throughout the study. Further details can be found in the protocol, Section 6.4. The timing for statistical analysis is specified in Section 7.3.

5.1. Hypotheses and Decision Rules

5.1.1. Immunogenicity Hypotheses

Cohort 1, Cohort 2, and Cohort 4: For objectives evaluated separately within Cohort 1, Cohort 2, and Cohort 4, there is no formal hypothesis testing. All statistical analyses will be descriptive.

Cohort 2 and Cohort 3 combined:

Superiority and Noninferiority of Anti-Omicron Immune Responses

For the >55-year age group (Cohort 2/Group 4 + Cohort 3/Group 2 combined):

The primary immunogenicity objective is to assess the superiority with respect to level of neutralizing titer and noninferiority with respect to seroresponse rate of the anti-Omicron

BA.4/BA.5 immune response induced by BNT162b2 Bivalent (WT/OMI BA.4/BA.5) 30 μ g in the >55-year age group relative to the anti-Omicron immune response elicited by BNT162b2 30 μ g in the >55-year age group from C4591031 Substudy E.

The primary objective will be evaluated by the following 2 hypotheses:

• The first null hypothesis (H₀) is

$$H_0$$
: $\ln(\mu_1) - \ln(\mu_2) \le \ln(1)$ vs H_1 : $\ln(\mu_1) - \ln(\mu_2) > \ln(1)$

where ln(1) corresponds to a 1-fold margin for superiority and

- o Ln(μ_1) is the natural log of the geometric mean of SARS-CoV-2 Omicron (sublineage BA.4/BA.5)—neutralizing titer measured at 1 month after BNT162b2 Bivalent (WT/OMI BA.4/BA.5) 30 µg given as a second booster dose in the >55-year age group (Cohort 2/Group 4 + Cohort 3/Group 2);
- o $Ln(\mu_2)$ is the natural log of the geometric mean of SARS-CoV-2 Omicron (sublineage BA.4/BA.5)—neutralizing titer measured at 1 month after BNT162b2 given as a second booster dose in the >55-year age group from C4591031 Substudy E.
- The second null hypothesis (H₀) is

$$H_0: p_1 - p_2 \le -0.05 \text{ vs } H_1: p_1 - p_2 > -0.05$$

where -5% is the noninferiority margin for seroresponse and

- ο p_1 is the percentage of participants with seroresponse to the Omicron strain (sublineage BA.4/BA.5) at 1 month after BNT162b2 Bivalent (WT/OMI BA.4/BA.5) 30 µg given as a second booster dose in the >55-year age group (Cohort 2/Group 4 + Cohort 3/Group 2);
- o p_2 is the percentage of participants with seroresponse to the Omicron strain (sublineage BA.4/BA.5) at 1 month after BNT162b2 given as a second booster dose in the >55-year age group from C4591031 Substudy E.

Seroresponse is defined as achieving a \geq 4-fold rise from baseline (before the study vaccination). If the baseline measurement is below the LLOQ, the postvaccination measure of \geq 4 × LLOQ is considered seroresponse.

Superiority based on GMR will be declared if the lower limit of the 2-sided 95% CI for the GMR is greater than 1; noninferiority based on seroresponse will be declared if the lower limit of the 2-sided 95% CI for the difference in percentages of participants with seroresponse is >-5%.

For the 18- to 55-year age group (Cohort 2/Group 2 + Cohort 3/Group 1 combined):

The primary immunogenicity objective is to assess the noninferiority with respect to level of neutralizing titer and seroresponse rate of the anti-Omicron BA.4/BA.5 immune response induced by BNT162b2 Bivalent (WT/OMI BA.4/BA.5) 30 μ g in the 18- to 55-year age group (Cohort 2/Group 2 + Cohort 3/Group 1) relative to the anti-Omicron immune response elicited by BNT162b2 Bivalent (WT/OMI BA.4/BA.5) 30 μ g in the >55-year age group (Cohort 2/Group 4 + Cohort 3/Group 2). The primary objective will be evaluated by the following 2 hypotheses:

• The first null hypothesis (H₀) is

$$H_0$$
: $\ln(\mu_1) - \ln(\mu_2) \le \ln(0.67)$ vs H_1 : $\ln(\mu_1) - \ln(\mu_2) > \ln(0.67)$

where ln(0.67) corresponds to a 1.5-fold margin for noninferiority and

- o Ln(μ_1) is the natural log of the geometric mean of SARS-CoV-2 Omicron (sublineage BA.4/BA.5)—neutralizing titer measured at 1 month after BNT162b2 Bivalent (WT/OMI BA.4/BA.5) 30 µg given as a second booster dose in the 18- to 55-year age group (Cohort 2/Group 2 + Cohort 3/Group 1);
- Cublineage BA.4/BA.5)—neutralizing titer measured at 1 month after BNT162b2 Bivalent (WT/OMI BA.4/BA.5) ag given as a second booster dose in the >55-year age group (Cohort 2/Group 4 + Cohort 3/Group 2).
- The second null hypothesis (H₀) is

$$H_0: p_1 - p_2 \le -0.1 \text{ vs } H_1: p_1 - p_2 > -0.1$$

where -10% is the noninferiority margin for seroresponse and

- p₁ is the percentage of participants with seroresponse to the Omicron strain (sublineage BA.4/BA.5) at 1 month after BNT162b2 Bivalent (WT/OMI BA.4/BA.5) 30 μg given as a second booster dose in the 18- to 55-year age group (Cohort 2/Group 2+ Cohort 3/Group 1);
- p_2 is the percentage of participants with seroresponse to the Omicron strain (sublineage BA.4/BA.5) at 1 month after BNT162b2 Bivalent (WT/OMI BA.4/BA.5) 30 μg given as a second booster dose in the >55-year age group (Cohort 2/Group 4 + Cohort 3/Group 2).

Seroresponse is defined as achieving a \geq 4-fold rise from baseline (before the study vaccination). If the baseline measurement is below the LLOQ, the postvaccination measure of \geq 4 × LLOQ is considered seroresponse.

Noninferiority based on GMR will be declared if the lower limit of the 2-sided 95% CI for the GMR is greater than 0.67; noninferiority based on seroresponse will be declared if the lower limit of the 2-sided 95% CI for the difference in percentages of participants with seroresponse is >-10%.

Noninferiority of Anti–Reference-Strain Immune Responses

The secondary immunogenicity objective is to assess the noninferiority of the anti–reference-strain immune response induced by BNT162b2 Bivalent (WT/OMI BA.4/BA.5) 30 µg in the >55-year age group relative to the anti–reference strain immune response elicited by BNT162b2 30 µg in the >55-year age group from C4591031 Substudy E. The noninferiority objective will be evaluated by the following hypothesis:

• The null hypothesis (H₀) is

$$H_0$$
: $\ln(\mu_1) - \ln(\mu_2) \le \ln(0.67)$ vs H_1 : $\ln(\mu_1) - \ln(\mu_2) > \ln(0.67)$

where ln(0.67) corresponds to a 1.5-fold margin for noninferiority and

- o Ln(μ_1) is the natural log of the geometric mean of SARS-CoV-2 reference-strain-neutralizing titers measured at 1 month after BNT162b2 Bivalent (WT/OMI BA.4/BA.5) 30 µg given as a second booster dose in the >55-year age group (Cohort 2/Group 4 + Cohort 3/Group 2);
- o Ln(μ_2) is the natural log of the geometric mean of SARS-CoV-2 reference-strain-neutralizing titers measured at 1 month after BNT162b2 given as a second booster dose in the >55-year age group from C4591031 Substudy E.

Noninferiority based on the GMR will be declared if the lower limit of the 2-sided 95% CI for the GMR is greater than 0.67 (1.5-fold criterion) and the point estimate of the GMR is \geq 0.8.

5.1.2. Multiplicity Adjustment

Cohort 1, Cohort 2, and Cohort 4: No multiplicity adjustment is needed for objectives evaluated separately within Cohort 1, Cohort 2, and Cohort 4, as there are no statistical hypotheses.

Cohort 2 + Cohort 3 combined:

The primary and secondary objectives will be evaluated sequentially using a 1-sided alpha of 0.025. The primary objective for the >55-year age group (with respect to the anti-Omicron BA.4/BA.5 immune response) will be evaluated first, followed by the secondary objective of the GMR for the >55-year age group (with respect to the anti-reference-strain immune response), and then the primary objective for the 18- to 55-year age group (with respect to the anti-Omicron BA.4/BA.5 immune response). The later objective will be evaluated only if the previous objective is met.

The primary objectives involve 2 hypotheses: GMR and seroresponse rate difference. Both hypotheses within the objective must be established before evaluating the next objective in the sequence. Therefore, the overall type I error is fully controlled.

5.2. General Methods

CIs for all endpoints in the statistical analysis will be presented as 2-sided at the 95% level unless specified otherwise.

5.2.1. Analyses for Binary Endpoints

Descriptive statistics for categorical variables (eg, proportions) are the percentage (%), the numerator (n) and the denominator (N) used in the percentage calculation, and the 95% CIs, where applicable.

The exact 95% CI for binary endpoints for each group will be computed using the F distribution (Clopper-Pearson method). The 95% CI for the between-group difference for binary endpoints will be calculated using the Miettinen and Nurminen method. 2

The primary approach to calculate the difference in seroresponse rate between 2 groups and the associated 95% CI will be based on Miettinen and Nurminen method stratified by baseline neutralizing titer category (< median, ≥ median). The median of baseline neutralizing titers will be calculated based on the pooled data in 2 comparator groups.

5.2.2. Analyses for Continuous Endpoints

Unless otherwise stated, descriptive statistics for continuous variables are n, mean, median, standard deviation, minimum, and maximum.

5.2.3. Geometric Means

The geometric means will be calculated as the mean of the assay results after making the logarithm transformation and then exponentiating the mean to express results on the original scale. Two-sided 95% CIs will be obtained by taking log transforms of assay results, calculating the 95% CI with reference to Student's t distribution, and then exponentiating the confidence limits.

5.2.4. Geometric Mean Ratios

Model-Based GMR:

As the primary approach, the GMR and associated 95% CI will be calculated by exponentiating the difference in LS means and the corresponding CIs based on analysis of logarithmically transformed assay results using a linear regression model that includes terms for baseline neutralizing titer and comparison group.

Unadjusted GMR:

The GMR will be calculated as the mean of the difference of logarithmically transformed assay results and exponentiating the mean. Two-sided CIs will be obtained by calculating CIs using Student's t distribution for the mean difference of the logarithmically transformed assay results and exponentiating the confidence limits.

5.2.5. Geometric Mean Fold Rises

GMFRs are defined as ratios of the results after vaccination to the results before vaccination. GMFRs are limited to participants with nonmissing values at both time points.

GMFRs will be calculated as the mean of the difference of logarithmically transformed assay results (later time point minus earlier time point) and exponentiating the mean. The associated 2-sided 95% CIs will be obtained by constructing CIs using Student's t distribution for the mean difference on the logarithm scale and exponentiating the confidence limits.

5.2.6. Reverse Cumulative Distribution Curves

Empirical RCDCs will plot proportions of participants with values equal to or exceeding a specified assay value versus the indicated assay value, for all observed assay values. Data points will be joined by a step function with data points on the left side of the step.

5.3. Methods to Manage Missing Data

A partial AE start date (missing day or missing both month and day) will be imputed by assigning the earliest possible start date using all available information, such as the stop date of the AE and the study vaccination date(s) from the same participant, following the Pfizer standard for handling an incomplete AE start date. A complete missing start date for an AE is not allowed in the data collection.

Missing serology results will not be imputed. Immunogenicity results that are below the LLOQ will be set to $0.5 \times \text{LLOQ}$ in the analysis; this may be adjusted once additional data on the assay characteristics become available.

No additional imputation will be applied to other missing data.

6. ANALYSES AND SUMMARIES

6.1. Primary Endpoint(s)

6.1.1. Primary Safety Endpoints

All primary safety endpoints will be summarized by age group (as applicable) and vaccine group for Cohort 1, Cohort 2, Cohort 2 and Cohort 3 combined (Cohort 2/Group 2 + Cohort 3/Group 1 combined and Cohort 2/Group 4 + Cohort 3/Group 2 combined), and Cohort 4.

6.1.1.1. Local Reactions

6.1.1.1.1. Main Analysis

- Estimands: The percentage of participants reporting local reactions (redness, swelling, and pain at the injection site) for up to 7 days after the study vaccination (Section 2.2).
- Analysis set: Safety population (Section 4).
- Analysis time point: Up to 7 days after the study vaccination.
- Analysis methodology: Descriptive statistics (Section 5.2.1).
- Intercurrent events and missing data: The participants without any e-diary or unplanned clinical assessment data and without reactogenicity data reported in the AE CRF throughout the 7 days after vaccination will be excluded from the analysis; completely missing reactogenicity data (ie, all 7 days of collection are missing) will not be imputed. For the partially missed reactogenicity data (ie, 1-6 days of reactogenicity data are available), it is assumed that no reactions or events were experienced on the missing days.
- Reporting results: Descriptive statistics for each and any local reaction after the study vaccination in each group will be presented by maximum severity and cumulatively across severity levels. Descriptive summary statistics will include counts and percentages of participants with the indicated endpoint and the associated 2-sided Clopper-Pearson 95% CIs.

6.1.1.1.2. Supplemental Analysis

To support the assessment of local reactions, the following endpoints (as defined in Section 3.1.1.1) will be summarized with the same analysis time point and analysis population as above, and appropriate analysis methodology and reporting results:

- Duration (days) of each local reaction after the study vaccination.
- Onset day of each local reaction after the study vaccination.

These continuous endpoints will be summarized by displaying n, mean, median, standard deviation, minimum, and maximum by group.

Figures:

Bar charts with the proportions of participants for each local reaction throughout 7 days after the study vaccination will be plotted by group. The bars will be divided into severity categories to highlight the proportions of participants by maximum severity.

6.1.1.2. Systemic Events

6.1.1.2.1. Main Analysis

- Estimands: The percentage of participants reporting systemic events (fever, fatigue, headache, chills, vomiting, diarrhea, new or worsened muscle pain, and new or worsened joint pain) for up to 7 days after the study vaccination (Section 2.2).
- Analysis set: Safety population (Section 4).
- Analysis time point: Up to 7 days after the study vaccination.
- Analysis methodology: Descriptive statistics (Section 5.2.1).
- Intercurrent events and missing data: The participants without any e-diary or unplanned clinical assessment data and without reactogencity events reported in the AE CRF throughout the 7 days after vaccination will be excluded from the analysis; completely missing reactogenicity data (ie, all 7 days of collection are missing) will not be imputed. For the partially missed reactogenicity data (ie, 1-6 days of reactogenicity data are available), it is assumed that no reactions or events were experienced.
- Reporting results: Descriptive statistics for each systemic event after the study
 vaccination in each group will be presented by maximum severity and cumulatively
 across severity levels. Descriptive summary statistics will include counts and
 percentages of participants with the indicated endpoint and the associated 2-sided
 Clopper-Pearson 95% CIs.

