Section 1.3 Schedule of Activities, Section 8.4.8 Adverse Events of Special Interest, and Section 8.10.11 Additional Procedures for Monitoring of Potential Pericarditis or Myocarditis	Updated to: - extend monitoring of cardiac symptoms through 6 weeks after study intervention administration amend wording for cardiologist evaluation classify the diagnosis of myocarditis of pericarditis as an important medical event requiring reporting as an SAE.	Per feedback from FDA/CBER.	Substantial
Section 5.2 Exclusion Criteria and Section 6.9.1 Prohibited During the Study	Updated to clarify exclusion of monoclonal antibodies.	To clarify and align with other C459 protocols based on site feedback.	Nonsubstantial
Section 8.3.4 Electronic Diary	Added text related to e-diary reminder notifications and capture of missed diary data in CRF.	To include in the protocol per FDA/CBER feedback.	Nonsubstantial
Section 8.10.1 Visit 1 - Study Intervention Administration - Day 1	Updated text related to IRT notifications.	To clarify which IRT notifications are received by blinded versus unblinded team members.	Nonsubstantial
Section 9.1.1 Estimands	Updated to remove "e-diary" when referencing reactogenicity data.	To align with data handling where reactogenicity data are compiled from the e-diary and CRF.	Nonsubstantial
Section 10.8 Appendix 8: Protocol Amendment History	Added Amendment 4 summary of changes. Clarified Amendment 3 and Amendment 5.	Protocol template requirement.	Nonsubstantial
Section 10.9 Appendix 9: Abbreviations	Updated with the BNT162b6 vaccine.	Administrative updates for the addition of the BNT162b6 vaccine to the protocol.	Nonsubstantial

Section # and Name	Description of Change	Brief Rationale	Substantial or Nonsubstantial
Section 11 References	Additional references for epidemiological data and new variant mutations.	To support statements made throughout the synopsis and introduction.	Nonsubstantial
All	Added reference to PSSA for reporting of safety information to Pfizer Safety and edited text in line with current process.	To capture reporting process to Pfizer Safety via PSSA.	Nonsubstantial
All	Removal of reference to "booster" in Cohort 4 and in relation to current public health vaccination schedule text.	To align with recent simplified public health vaccination schedules.	Nonsubstantial

TABLE OF CONTENTS

LIST OF TABLES	11
1. PROTOCOL SUMMARY	12
1.1. Synopsis	12
1.2. Schema	32
1.3. Schedule of Activities	33
2. INTRODUCTION	41
2.1. Study Rationale	41

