1. VERSION HISTORY

Table 1. Summary of Changes

Version/ Date	Associated Protocol	Rationale	Specific Changes
1 12 Jul 2022	Original 24 Jun 2022	N/A	N/A
2 15 Sep 2022	Protocol amendment 1 (PA1), 27 Jul 2022	Adjusted the study design to include pediatric participants; removed the blinding level and changed Phase 2 to Phase 2/3	1. Changed the title, Section 2.3, Section 3.1.1.5, Section 7, and Figure 1.
	Protocol amendment 2 (PA2), 24 Aug 2022	Added primary safety and immunogenicity objectives, endpoints, and estimands for each cohort	2. Changed Section 2.2, Section 3.1.1, Section 3.1.2, Section 6.1.1, and Section 6.1.2
		3. Added secondary objectives, endpoints, and estimands	3. Changed Section 2.2 and Section 3.2; added Section 6.2
		4. Added exploratory objectives, endpoints, and estimands for each cohort	4. Changed Section 2.2, Section 3.3, and Section 6.3
		5. Changed the reporting of COVID-19 symptoms in the event of a positive COVID-19 test result. Included information about participants taking medications intended to treat COVID-19	5. Changed Section 3.1.1.2 and Section 3.4.3
		6. Made adjustments to the general statistical methods	6. Added Section 5.1 and Section 5.2.4; changed Section 5.2.1
		7. Adjusted analyses timing in accordance with regulatory agency's feedback	7. Changed Section 7.3
		8. Deleted "vaccine" when in front of "group;" added "assigned" with "randomized"; removed "Omicron sublineages"	Changed throughout the document

Table 1. Summary of Changes

Version/ Date	Associated Protocol	Rationale	Specific Changes
3 14 Nov 2022	N/A	Per CBER request, clarify how to calculate median baseline titer level for the analysis of the differences in seroresponse rates using the Miettinen and Nurminen method stratified by the baseline titer category (<median or="" td="" ≥median)<="">Changed Section 5.2.1 and Section 6.1.2.2.1	</median>	Changed Section 5.2.1 and Section 6.1.2.2.1
4 03 Aug 2023	Protocol amendment 6 (PA6), 27 Jul 2023	 Updates in the protocol title Added design, objective, and analysis for Cohort 4 Split the analysis time points for primary/secondary immunogenicity objectives and exploratory objectives Clarified consolidation of reactogenicity events recorded on the AE CRF with e-diary data for reactogenicity summary 	~ i

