3.1.1.1. Local Reactions

The local reactions assessed and reported in the e-diary are redness, swelling, and pain at the injection site, from Day 1 through Day 7 after the study vaccination, where Day 1 is the day of the study vaccination. The e-diary entries from the participant and unplanned clinical assessments within 7 days after vaccination will be the primary data sources for these events. In addition, any events recorded on the AE CRF that are considered local reactions within 7 days after vaccination will be consolidated with e-diary data and included in the reactogenicity report. This section describes derivations with details for the assessment of local reactions: presence, severity level, duration, and onset day.

Presence or Absence

For each local reaction and any local reaction on any day, Table 3 explains the algorithm to derive the presence of a reaction (yes or no) during the interval from Day 1 through Day 7, where Day 1 is the day of the study vaccination.

Table 3. Derived Variables for Presence of Each and Any Local Reaction Within 7 Days for the Study Vaccination

Variable	Yes (1)	No (0)
Presence of each local reaction on any day.	reaction as "yes" on any	Participant reports the reaction as "no" on all 7 days (Day 1 through Day 7) or as a combination of "no" and missing on all 7 days (Day 1 through Day 7).
Presence of any local reaction on any day.	reaction as "yes" on any	For all 3 local reactions, participant reports "no" on all 7 days (Day 1 through Day 7) or as a combination of "no" and missing on all 7 days (Day 1 through Day 7).

Note: Completely missing e-diary data will not be imputed. Participants with no e-diary data reported will not be included in the e-diary summaries.

Severity and Maximum Severity

Redness and swelling will be measured and recorded in measuring device units (range: 1 to 21) and then categorized during analysis as absent, mild, moderate, or severe based on the grading scale in Table 4. Measuring device units can be converted to centimeters according to the following formula: 1 measuring device unit = 0.5 cm. Pain at the injection site will be assessed by the participant as absent, mild, moderate, or severe according the grading scale in Table 4.

For events recorded in the AE CRF that are considered local reactions and consolidated with e-diary data, the severity will be based on the AE intensity grade recorded in the CRF.

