3.1.1.2. Systemic Events

The systemic events assessed and recorded in the e-diary are fatigue, headache, chills, vomiting, diarrhea, new or worsened muscle pain, and new or worsened joint pain within 7 days after the study vaccination. The e-diary entries from the participant and unplanned clinical assessments within 7 days after vaccination will be the primary data sources for these events. In addition, any events recorded on the AE CRF that are considered systemic events starting within 7 days after vaccination will be consolidated with e-diary data and included in the reactogenicity report. The derivations for systemic events will be handled similar to the way local reactions are handled for presence of event, severity level, duration, and onset day (see Section 3.1.1.1).

The symptoms will be assessed by the participant as absent, mild, moderate, or severe according to the grading scale in Table 5 and recorded in the e-diary. For events recorded in the AE CRF that are considered systemic events and consolidated with e-diary data, the severity will be based on the AE intensity grade recorded in the CRF.

If a Grade 3 systemic event is reported in the reactogenicity e-diary, a telephone contact should occur to ascertain further details and determine whether a site visit is clinically indicated. Only an investigator or medically qualified person is able to classify a participant's systemic event as Grade 4. If a participant experiences a confirmed Grade 4 systemic event, the investigator must immediately notify the sponsor.

Table 5. Systemic Event Grading Scale

	Mild (Grade 1)	Moderate (Grade 2)	Severe (Grade 3)	Potentially Life-Threatening (Grade 4)
Vomiting	1-2 times in 24 hours	>2 times in 24 hours	Requires IV hydration	Emergency room visit or hospitalization for hypotensive shock
Diarrhea	2 to 3 loose stools in 24 hours	4 to 5 loose stools in 24 hours	6 or more loose stools in 24 hours	Emergency room visit or hospitalization for severe diarrhea

Table 5. Systemic Event Grading Scale

	Mild (Grade 1)	Moderate (Grade 2)	Severe (Grade 3)	Potentially Life-Threatening (Grade 4)
Headache	Does not interfere with activity	Some interference with activity	Prevents daily routine activity	Emergency room visit or hospitalization for severe headache
Fatigue/tiredness	Does not interfere with activity	Some interference with activity	Prevents daily routine activity	Emergency room visit or hospitalization for severe fatigue

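### The SAP gives two denominators for 7-day reactogenicity, and under the main-analysis rule a participant with no diary and no unplanned assessment is counted only if an event is on the AE CRF

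*SAP*

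**What the plan says.** Local reactions and systemic events within 7 days are primary safety endpoints for all analysis groups (SAP 3.1.1). They are reported as percentages with Clopper-Pearson 95% CIs. Two places in the SAP settle who is counted.

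- **Derivation.** The note under Table 3 in SAP 3.1.1.1 says: "Participants with no e-diary data reported will not be included in the e-diary summaries". SAP 3.1.1.2 carries this over to systemic events: "The derivations for systemic events will be handled similar to the way local reactions are handled for presence of event".
- **Main analysis.** SAP 6.1.1.1.1 applies a three-source test. Participants with no diary, no unplanned assessment and "without reactogenicity data reported in the AE CRF throughout the 7 days after vaccination will be excluded from the analysis". SAP 6.1.1.2.1 has the same test for systemic events, naming "The participants without any e-diary or unplanned clinical assessment data and without reactogencity events reported in the AE CRF".

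SAP 3.1.1.1 also says that e-diary entries and "unplanned clinical assessments within 7 days after vaccination will be the primary data sources for these events", and it merges reactogenicity events from the AE CRF into the same report. That merging was intended: the SAP version 4 history lists "Clarified consolidation of reactogenicity events recorded on the AE CRF with e-diary data for reactogenicity summary", and the protocol amendment 6 summary of changes gives a matching reason for Section 9.1.1, "To align with data handling where reactogenicity data are compiled from the e-diary and CRF".

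Protocol 8.3.4 explains how such an event reaches the AE page: the participant did not enter it in the diary and told the site instead. No corresponding entry for the absence of a reaction is described.

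**The concern.** There are two linked problems.

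1. A participant with no diary data but with an unplanned assessment or a CRF event is out under the Table 3 note and in under the main-analysis sections. Two programmers working from different sections could produce different denominators for a primary safety percentage.
2. Under the main-analysis rule, a participant with neither diary nor unplanned assessment can enter only through the AE CRF. Non-transmitters with a recorded event are counted and non-transmitters without one are dropped. Each such entry adds one to both the numerator and the denominator of the any-reaction percentage, and no event-free non-transmitter offsets it. Groups with different transmission rates could then differ for that reason alone.

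The scoring of these participants is also open. Someone known only from one CRF event has reported nothing about the other symptoms. The SAP does not say whether those symptoms count as absent or missing, nor whether a systemic event on the CRF brings the participant into the local-reaction denominator.

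**Working it through.** The documents state no reactogenicity rate, non-transmission rate or CRF-capture rate, so there is no planned figure to reproduce. The calculation below shows the size under stated assumptions.

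**Inputs (all assumed)**
- p = 0.60, any-reaction rate in participants with a diary
- m = 0.05, share with no diary and no unplanned assessment (also 0.02 and 0.10)
- q = 0.40, 0.60 or 0.80, rate in those participants
- c = 0.50 or 1.00, share of their events that reach the AE CRF
- diaries otherwise complete

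**Formulas**
- Table 3 note: p
- Main-analysis rule: [(1-m)p + mqc] / [(1-m) + mqc]
- Truth: (1-m)p + mq

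**One case in full** (m = 0.05, q = 0.60, c = 1): (0.57 + 0.03) / (0.95 + 0.03) = 0.60/0.98 = 61.2%.

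| q (m = 0.05) | Truth | Table 3 note | Main rule, c = 0.5 | Main rule, c = 1 |
|---|---|---|---|---|
| 0.40 | 59.0% | 60.0% | 60.4% | 60.8% |
| 0.60 | 60.0% | 60.0% | 60.6% | 61.2% |
| 0.80 | 61.0% | 60.0% | 60.8% | 61.6% |

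The rules differ by 0.4 to 1.6 points. At q = 0.80 the main rule is nearer the truth: it is 0.2 points low or 0.6 high, while the Table 3 note is 1.0 low. At q = 0.40 or 0.60 the Table 3 note is nearer.

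**Other non-transmission rates** (q = 0.60): m = 0.02 gives 60.2-60.5%, and m = 0.10 gives 61.3-62.5%. Two groups with the same 60% rate, one at 2% and one at 10% non-transmission, would differ by 62.5 - 60.5 = 2.0 points at full capture.

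**Wider grid, equal rates in both sets** (non-transmission 2-10%, event rate 10-80%, capture 25-100%): the shift runs from 0.05 to 2.63 points. The largest is at 10%, 50% and 100%; with 60 participants that is 27/54 = 50.0% against 30/57 = 52.6%.

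**As counts** (n = 300, 15 non-transmitters, equal rates):
- Table 3 note: 171/285 = 60.0% (95% CI 54.1-65.7)
- Main rule, all 9 events on the CRF: 180/294 = 61.2% (55.4-66.8)
- Main rule, 5 of the 9 on the CRF: 176/290 = 60.7% (54.8-66.3)

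For a Cohort 4 arm of 60, 36/60 = 60.0% has a CI of 46.5-72.4.

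**Single symptom.** Let a be the share of non-transmitters admitted and x the share with this symptom on the CRF, and score admitted participants without it as event-free. The estimate is [(1-m)p + mx] / [(1-m) + ma]. With m = 0.05, p = 0.50 and a = 0.60:
- x/a = 1/3: (0.475 + 0.010)/0.98 = 49.5%
- x/a = 0.8: (0.475 + 0.024)/0.98 = 50.9%

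For one symptom, even the sign of the difference between the rules is not fixed.

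**Can the number involved be recovered?** SAP 5.2.1 reports n and N for each percentage, and SAP 6.5.2.3 counts non-transmitters in the safety population. In the example, 294 - (300 - 15) = 9 were admitted without a diary. This is approximate, because SAP 3.4.2 treats a diary holding only antipyretic data as transmitted. The split between AE CRF and unplanned-assessment entrants cannot be recovered.

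**The case against.** The strongest reply is that the main-analysis sections govern. They state who is excluded from the analysis, while the Table 3 note speaks of e-diary summaries and sits under a derivation table. This gives a programmer a reasonable answer, and the remedy may keep that rule as main. It does not remove the conflict: the SAP describes no separate diary-only reactogenicity table, and the note is attached to the presence variable that the main analysis reports. Nor does it touch the outcome dependence, which lies in the main-analysis rule itself.

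Several further points stand.
- Merging CRF events was deliberate and is not disputed.
- Table 3 does not say that a negative report must come from the diary, so an unplanned assessment could supply one.
- Entry through an unplanned assessment without a diary is probably rare. Protocol 8.10.6 ties such visits mainly to Grade 3 or suspected Grade 4 diary reports; the other way in is a participant calling about severe symptoms (Protocol 8.10.1 and 8.10.2). That route is itself largely triggered by the outcome.
- Sites review diaries often, ideally daily, which should limit non-transmission.

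A reader might infer that the number of participants involved is hidden. It is not: the total is approximately derivable from planned outputs, and only the split by route is missing. A reader might also see a different missing-day rule in SAP 6.1.1.2.1, whose sentence stops before the words on missing days. That is clerical, since SAP 2.2, SAP 4 and Protocol 9.1.1 give the full rule for all reactogenicity data.

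**Conclusion.** The point holds. The SAP states two denominators for a primary safety percentage, and the main-analysis rule admits non-transmitters by outcome. The effect is probably small: about 0.4 to 1.6 points for any reaction at a 60% rate, 5% non-transmission and 50-100% CRF capture. Every one of those inputs is an assumption. The shift is well inside the confidence interval in the examples above.

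A reader might conclude that the main-analysis rule always overstates reactogenicity, or that the Table 3 rule is the correct one. Neither follows. If non-transmitters react more often, the diary-only figure is too low and can be the worse of the two; for a single symptom the direction is open.

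The endpoints are descriptive, so no test or alpha is involved. The AE and SAE percentages (SAP 6.1.1.3.1 and 6.1.1.4.1) do not use this rule. The change is worth making because a primary percentage needs one reproducible denominator and the cost is low.

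**What to change.** 1. Reconcile the Table 3 note with SAP 6.1.1.1.1 and 6.1.1.2.1 so that one denominator applies. The three-source rule may stay as main. Name one rule for scoring the remaining local and systemic items of a participant known only from the AE CRF or an unplanned assessment.
2. Add one supporting table of the reactogenicity percentages with a denominator that does not depend on outcome: participants with at least 1 day of e-diary data for the relevant local or systemic items. The transmission definition in SAP 3.4.2 does not serve, because an antipyretic-only diary passes it.
3. Footnote the main table, by group, with the number who enter only through the AE CRF and the number who enter only through an unplanned assessment.

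The cost is a few sentences in the SAP, one programming flag and one extra table. Data collection does not change, and CRF events stay in the main summary.
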